### 2.1.1 Primary Objective

The primary objective of this study is to determine the diagnostic utility of the BIOMONITOR to detect AF within study subjects who are being evaluated for an ablation. Specifically, the diagnostic sensitivity of the BIOMONITOR will be determined by comparing AF events detected by the BIOMONITOR and 48 hr Holter monitor for each subject. Using the 48 hr Holter monitor as the gold standard, subjects with AF events detected by the BIOMONITOR will be categorized as true positive or false positive.

It is expected that sensitivity will be greater than 90% in detecting AF within study subjects that are being evaluated for ablations.

Diagnostic Sensitivity:

$H_0$ : The Sensitivity (Se) for detecting at least one true positive AF episode per subject will be less than or equal to 90%. ( $Se \leq 90\%$ )

$H_a$ : The Sensitivity for detecting at least one true positive AF episode per subject will be greater than 90% ( $Se > 90\%$ )

A rejection of the null hypothesis would demonstrate that there is evidence that Sensitivity is greater than 90%.

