### 2.5.1 Objective Analysis

The primary objective analysis will calculate the diagnostic sensitivity of the BIOMONITOR. Diagnostic sensitivity is the ability of the BIOMONITOR to correctly identify subjects who have AF as determined by the Holter monitor.

Specifically, diagnostic sensitivity is determined as:

$$\text{Diagnostic sensitivity} = \frac{\text{Number of TP patients}}{\text{Number of TP} + \text{Number of FP patients}}$$

Where TP is true positive and FP is false positive.

To test the primary hypotheses, sensitivity will be calculated and a one-tailed binomial test will be implemented to determine if there is evidence to support the rejection of the null hypothesis.

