### 2.5.2 Analysis for Data of Interest

Additional data of interest, which includes the characterization of the insertion procedure and device functionality, will be analyzed quantitatively and statistically where appropriate. All available results will be categorized and summarized.

Data from the 48 hr Holter recording will support metrics including sensitivity, specificity, positive predictive value, and negative predictive value. Holter monitoring will be used as the gold standard for AF detection. Sensitivity is defined as the proportion of true positives that are correctly identified as positive. Specificity is defined as the proportion of true negatives that are correctly identified as negative. The positive predictive value is defined as the proportion of positive detected episodes that are true positive. The negative predictive value is defined as the proportion of negative detected episodes that are true negative. Evaluation may be performed on an episode, subject, or duration basis. Additional, non-AF episodes recorded on the BIOMONITOR may be compared to Holter data to confirm the onset of different arrhythmias.

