### 2.5.3 Analysis Population

The analysis population for the primary objective includes all subjects that are enrolled in the study and have evaluable 48 hr Holter data and BIOMONITOR data. If an evaluable 48 hr Holter contains segments which are marked as not interpretable by the Holter Core Laboratory, these segments will be excluded from analysis. Subjects may be allowed to repeat 48 hr Holter monitoring if the Holter Core Laboratory determines a significant portion of the recording is uninterpretable.

Evaluable BIOMONITOR data is defined as successful collection of the complete BIOMONITOR data set from the 48 hr Holter period. In the event that some BIOMONITOR detections are not available due to the number of detected events exceeding the device storage capacity, the segments with missing BIOMONITOR information will be excluded from the analysis.

Data of interest elements that require comparison to the 48 hr Holter monitor data will use the same analysis population. Analysis for additional data of interest will be completed with both provisionally enrolled and fully enrolled study populations.

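### The storage-overflow rule in Protocol 2.5.3 lets the BIOMONITOR's own output decide which interpretable Holter AF counts towards sensitivity

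*Protocol*

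**What the plan says.** Section 2.5.3 contains two exclusion rules. The first removes Holter segments that the core laboratory marks as not interpretable. The second applies when BIOMONITOR detections are unavailable "due to the number of detected events exceeding the device storage capacity"; in that case "the segments with missing BIOMONITOR information will be excluded from the analysis". The same section applies this population to every data-of-interest measure that needs comparison with the Holter.

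The overflow sentence follows directly on another statement: "Evaluable BIOMONITOR data is defined as successful collection of the complete BIOMONITOR data set from the 48 hr Holter period". A subject with overflow does not have a complete set, but the next sentence keeps that subject with segments removed.

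The reference standard is stated in 2.5.2: "Holter monitoring will be used as the gold standard for AF detection". Section 2.5.1 defines the primary measure in words: "Diagnostic sensitivity is the ability of the BIOMONITOR to correctly identify subjects who have AF as determined by the Holter monitor". Neither statement carries a condition on device memory. The hypothesis in 2.1.1 works per subject, needs at least one true positive episode, and has a null value of 90%. It is to be tested in this way: "a one-tailed binomial test will be implemented".

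**The concern.** The first rule depends on the quality of the reference recording. The second depends on the behaviour of the index test, because the time removed is the time in which the device had already recorded more events than it could hold. Time lost for that reason is unlikely to be a random sample of the 48 hours.

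If the dropped segments contain all of a subject's Holter AF, that subject changes from Holter-positive to Holter-negative and no longer contributes to sensitivity in the sense given in words. What is then estimated is sensitivity among subjects whose AF fell in time the device could store, which is not what 2.5.1 describes. Storage need not fill with true AF: section 1.3 lists bradycardia, sudden rate drop, high ventricular rate and asystole as recorded events too, and AF detections may be false.

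At stake is a primary test with few AF-positive subjects, in which the status of one subject can decide the result.

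**Working it through.** **Inputs.** From section 2.4: AF prevalence on Holter 50%, expected sensitivity 97%, precision 6.35%, 95% confidence, drop-out after Holter start 8%, sample size 60. From 2.1.1: null value 90%. The protocol states no alpha for the binomial test, so one-sided 0.05 is assumed and 0.025 is shown as well.

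**Step 1, the plan's own figure.** The AF-positive number for the stated precision is 1.96² × 0.97 × 0.03 / 0.0635² = 27.7. Dividing by 0.50 gives 55.4, and dividing by 0.92 gives 60.3. The stated 60 is reproduced, and the overflow rule does not alter it.

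**Step 2, expected AF-positive subjects.** If 60 subjects are evaluable, 60 × 0.50 = 30. If 60 start Holter monitoring and 8% drop out, 60 × 0.92 × 0.50 = 27.6. The earlier study in 1.2.1 found AF on Holter in 39 of 66 participants, three of whom had missing Holter data. That share would give 60 × 39/66 = 35 to 60 × 39/63 = 37.

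**Step 3, removing one subject counted as a miss.** With n AF-positive subjects and one miss, the exact one-sided p-value is n × 0.9^(n−1) × 0.1 + 0.9^n. With that subject removed it is 0.9^(n−1).

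| AF-positive subjects n | Subject kept as not detected | Subject removed | At 0.05 |
|---|---|---|---|
| 29 | 28/29, p = 0.199 | 28/28, p = 0.052 | fails both ways |
| 30 | 29/30, p = 0.184 | 29/29, p = 0.047 | fail becomes pass |
| 34 | 33/34, p = 0.133 | 33/33, p = 0.031 | fail becomes pass |
| 37 | 36/37, p = 0.104 | 36/36, p = 0.023 | fail becomes pass |
| 45 | 44/45, p = 0.052 | 44/44, p = 0.010 | fail becomes pass |
| 46 | 45/46, p = 0.048 | 45/45, p = 0.009 | passes both ways |

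The change from fail to pass occurs for every n from 30 to 45. At 28 positives it cannot occur, because even 28/28 gives p = 0.052.

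**Step 4, at 0.025.** With 30 or fewer positives no result rejects, since 30/30 gives p = 0.042. Because 0.9^35 = 0.02503 and 0.9^36 = 0.0225, a change from fail to pass first becomes possible at 37 positives.

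**Step 5, the opposite direction.** Suppose 29 subjects are positive and all were truly detected. Dropping one of them through overflow moves 29/29 (p = 0.047) to 28/28 (p = 0.052), so a pass becomes a fail. Suppose instead that a subject's only true detection is lost while other Holter AF remains in retained time. That subject becomes a miss, and 30/30 (p = 0.042) becomes 29/30 (p = 0.184).

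**The case against.** Several points on the other side stand.

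- **The device's result is unknown.** Overflow means that the device detected events and did not keep them. A reader might infer that the rule hides proven misses. The documents do not show that: in a lost segment the true AF may have been detected. Counting such a subject as not detected is a worst-case assumption.
- **The data may not be lost.** Section 1.3.1 describes triggered and daily Home Monitoring transmissions, so an episode missing from memory at 48 hours may already have been sent. Overflow is therefore not in itself a diagnostic failure.
- **The case is narrow.** The subject must overflow storage within 48 hours of memory being cleared (3.2.6), have no true positive among the retained recordings, and have all Holter AF in the lost time. Frequent true AF would usually leave a true positive behind.
- **The printed formula differs.** Section 2.5.1 prints TP/(TP+FP): "Where TP is true positive and FP is false positive". Under that formula a missed subject is never in the denominator and so cannot be removed from it. A subject with only false stored AF detections, whose true AF lies in dropped time, would count as a false positive and lower the ratio. The denominator argument here rests on the definition in words; the formula is a separate defect.
- **PPV and specificity.** A reader might also infer that the rule necessarily flatters these. It need not: dropping time rich in true AF removes true positives and can lower PPV. The PPV of 76.3% ± 38.7% in 1.2.1 comes from the first-generation device and says nothing about overflow.

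It can also be said that such detail belongs in a statistical analysis plan. That does not answer the point, because 2.5.3 already fixes the rule.

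**Conclusion.** The concern holds in a limited form. Section 2.5.3 excludes interpretable Holter time on the basis of the index test's own output, and this conflicts with the Holter-based definition of sensitivity in words in 2.5.1. Neither the direction nor the frequency of the bias can be derived from the protocol, because no overflow rate or storage limit is given. The p-values show what one subject could do, not what is expected.

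The possible consequence is large relative to the design. At an assumed one-sided 0.05, the handling of one subject counted as a miss turns a failed test into a passed one for 30 to 45 AF-positive subjects, a range that starts at the planned 30. At 28 positives, or at 0.025 with 30 or fewer, it cannot change the verdict. Effects on episode and duration measures are more likely than an effect on the primary test. The change is worth making because it is cheap, and because the result should not depend on device memory in either direction.

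**What to change.** In 2.5.3:

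1. Define each subject's Holter-AF status from all Holter time that the core laboratory can interpret, regardless of BIOMONITOR storage.
2. Before treating a detection as missing, look for it in sources already collected: the recording list saved at the completion visit (3.2.7) and the Home Monitoring transmissions.
3. For subjects whose only Holter AF lies in overflow segments that cannot be recovered, report sensitivity with them counted as not detected, alongside the segment-excluded result. State beforehand that the conclusion of sensitivity above 90% must hold under both.
4. Report the number of subjects and hours affected, and show the episode, duration, PPV and specificity measures both ways.
5. Reconcile the requirement for a complete BIOMONITOR data set with the overflow sentence that follows it.

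The cost is a change of wording and one extra tabulation, with no new data. The sensitivity that supports the claim may come out less favourable, and requiring both results makes the criterion somewhat stricter.

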### 2.5.4 Interim Analysis

In the BIO-Precision study, one interim analysis is planned and will occur once all eligible fully enrolled subjects have completed their 48 hr Holter monitoring visits. This analysis will assess the outcomes of the primary objective. At this interim analysis, the study objectives and additional data of interest may be evaluated to characterize initial results of the BIO-Precision Study.

## 3. PROTOCOL REQUIREMENTS

### 3.1 Patient Population

The investigator is responsible for screening all potential subjects and selecting those who are appropriate for study inclusion. Potential subjects will be evaluated to determine if they meet the inclusion and exclusion criteria described below in Sections 3.1.3 and 3.1.4. The subjects selected for participation should be from the investigator's general patient population according to the inclusion and exclusion criteria. Patients who require a legally authorized representative will not be allowed in the study.

#### 3.1.1 Indications

The BIOMONITOR is a SCRM that records subcutaneous ECG (sECG) and is indicated for:

- Patients with clinical syndromes or situations at increased risk of cardiac arrhythmias
- Patients who experience transient symptoms that may suggest a cardiac arrhythmia

The device has not been tested for and it is not intended for pediatric use.

#### 3.1.2 Contraindications

There are no known contraindications for the insertion of the BIOMONITOR. However, the patient's particular medical condition may dictate whether or not a subcutaneous, chronically inserted device can be tolerated.

#### 3.1.3 Inclusion Criteria

To support the objectives of this investigation, the inclusion criteria at the time of patient enrollment for this study include the following requirements:

- Meet the indications for SCRM insertion according to local regulations
- Patient is able to understand the nature of the study and provide written informed consent
- Inserted within the prior 30 days, or scheduled for insertion within 14 days, with BIOTRONIK's most current SCRM
- Diagnosed with paroxysmal atrial fibrillation and being evaluated for an AF ablation
- Agree to wearing a 48 hr Holter monitor
- Able and willing to complete all study visits at the study site for the study duration

- Able and willing to use a CardioMessenger® and accepts Home Monitoring concept
- Age greater than or equal to 18 years

### 3.1.4 Exclusion Criteria

To support the objectives of this investigation, the exclusion criteria at the time of patient enrollment include the following requirements:

- Patient meets none of the indications for a BIOMONITOR
- Patient is planned to have an ablation prior to BIOMONITOR insertion or 48 hr Holter monitoring visit
- Patient is currently diagnosed with long-standing persistent or permanent AF
- Patient is enrolled in another study that may change or alter the cardiac rhythm that occurs prior to the completion of the Holter
- Currently indicated for or implanted with a pacemaker, ICD device, or hemodynamic monitoring system
- Life expectancy less than 6 months
- Patients reporting pregnancy at the time of enrollment

For patients enrolled after BIOMONITOR insertion:

- R-wave sensing <0.25 mV according to the most recent Home Monitoring CardioReport or device interrogation available prior to enrollment

After the pre-Holter observation period but prior to 48 hr Holter monitoring initiation, confirm the absence of the following exclusion criteria based on the CardioReport collected at the end of the observation period:

- No AF episodes observed or transmitted during pre-Holter observation period
- R-wave sensing <0.25 mV during pre-Holter observation period as reported by the 24 hr mean or mean value since last follow-up

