## SUMMARY

Title	BIO-Precision Study
Descriptor	Assessment of the utility of BIOMONITOR to identify AF in ablation candidates using precise AF detection
Design	Prospective, multicenter, observational study
Purpose	The purpose of this study is to evaluate the diagnostic utility of BIOTRONIK's subcutaneous cardiac rhythm monitor (SCRM) for the detection of AF prior to an ablation procedure.
Subject Population	Study population includes patients diagnosed with paroxysmal AF being evaluated for an AF ablation.
Sample Size	This study will enroll up to 100 subjects, to obtain 60 usable Holter recordings.
Clinical Sites	Up to 5 U.S. sites.
Follow-up Period	All subjects will be followed for three months post 48 hr Holter monitoring.
Primary Objective	The primary objective of this study is to determine the diagnostic utility of the BIOMONITOR to detect AF within study subjects who are being evaluated for an ablation. Specifically, the diagnostic sensitivity of the BIOMONITOR will be determined by comparing AF events detected by the BIOMONITOR and 48 hr Holter monitor for each subject. Using the 48 hr Holter monitor as the gold standard, subjects with AF events detected by the BIOMONITOR will be categorized as true positive or false positive.
Study Risk Determination	Standard of care study including market released devices implanted according to FDA approved indications for use.
Sponsor	BIOTRONIK, Inc. Clinical Studies Department [name]

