**Figure 2: Enrollment Pre- and Post-BIOMONITOR insertion**

The primary analysis will focus on the utility of the BIOMONITOR for the detection of AF within patients who are being evaluated for an ablation. Data will be collected from in-person visits at study enrollment, BIOMONITOR insertion, and initiation and completion of 48 hr Holter monitoring. In addition, BIOMONITOR performance data will be collected throughout the study duration using BIOTRONIK Home Monitoring®, including a required Home Monitoring data check at the end of the pre-Holter observation period. Holter monitor recordings will be evaluated by a Holter Core Laboratory. In addition, BIOMONITOR detections may be adjudicated by an event adjudication committee, if applicable.

Figure 3 provides an overview of the clinical study design. Details of subject eligibility requirements are noted in Section 3.2.2 and details of other study specific procedures and data collection are noted in Section 3.2 and Section 4.

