## 3.2 Study Procedures

Subjects with a previously inserted BIOMONITOR will be provisionally enrolled once consent is given and will be considered fully enrolled once 48 hr Holter monitoring has been initiated. Subjects consented prior to insertion will be considered provisionally enrolled until the successful insertion of a BIOMONITOR and the initiation of 48 hr Holter monitoring.

BIOTRONIK Home Monitoring® should be activated in all subjects. Data will be collected at all visits starting at insertion (e.g. enrollment, Home Monitoring data check following the pre-Holter observation period, 48 hr Holter monitoring initiation and completion visit, and study exit). Enrollment data will include informed consent, subject demographics, and relevant medical history.

Insertion data will include procedure time, insertion location and orientation, and device serial numbers. Following insertion or at the time of enrollment, for subjects previously inserted with a BIOMONITOR, the BIOMONITOR must be programmed to the required programming settings to initiate the pre-Holter observation period.

Following the 12 to 16 day pre-Holter observation period, the presence of AF episodes and R-wave sensing performance will be evaluated. Subjects with no AF episodes during this time will not complete the Holter visit and will be exited from the study. Subjects with R-wave sensing <0.25 mV, as reported by the 24 hour mean or the mean value since last follow-up on the Home Monitoring CardioReport collected at the end of the pre-Holter observation period, will not complete 48 hr Holter monitoring and will be exited from the study.

For subjects presenting with at least one AF episode during the pre-Holter observation period, patient specific BIOMONITOR programming settings may be provided by BIOTRONIK prior to starting 48 hr Holter monitoring. Data will be collected at the 48 hr Holter monitoring initiation visit and will include Holter start time and selected programming. Data will also be collected at the completion of 48 hr Holter monitoring including the Holter recordings and all sECGs from the BIOMONITOR. The Holter data will be sent to the Holter Core Laboratory for evaluation.

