### **3.2.5 Pre-Holter Observation Period**

Subjects will undergo a 12 to 16 day pre-Holter observation period following enrollment, for subjects inserted with a BIOMONITOR prior to consent, or following insertion, for subjects consented prior to BIOMONITOR insertion. The BIOMONITOR must be programmed to the required programming settings either at enrollment or insertion, respectively. Subjects with a new BIOMONITOR device should be educated on the set up and use of the CardioMessenger to ensure Home Monitoring data is transmitted during the 12 to 16 day observation period. For subjects implanted before consent, Home Monitoring transmission status should be verified and any transmission issues resolved.

Following this pre-Holter observation period, a Home Monitoring data check will be performed and CardioReport obtained, containing a listing of all episode recordings. Information on AF episodes within the observation period will be collected. 48 hr Holter monitoring will not be performed for subjects with no AF episodes recorded or transmitted during the observation period or in subjects with R-wave sensing < 0.25 mV, as reported on the CardioReport collected at the completion of the observation period, and these subjects will exit the study. For subjects with AF episodes, BIOTRONIK may provide additional programming settings prior to initiation of 48 hr Holter monitoring.

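### The Holter is given only to subjects in whom the BIOMONITOR has already recorded or transmitted AF with adequate R-wave sensing, so the primary sensitivity is conditional on that filter, and the stated claim should say so

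*Protocol*

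**What the plan says.** After a 12 to 16 day observation period, a Home Monitoring data check decides who goes on to the reference test. Section 3.1.4 lists as an exclusion at that point "No AF episodes observed or transmitted during pre-Holter observation period", together with R-wave sensing below 0.25 mV. Section 3.2 states the consequence: "Subjects with no AF episodes during this time will not complete the Holter visit and will be exited from the study". Section 3.2.5 repeats it ("48 hr Holter monitoring will not be performed for subjects with no AF episodes recorded or transmitted during the observation period"), and 3.3.7 makes it a reason for withdrawal.

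Table 1 (Section 2.2) counts a subject as enrolled only once the Holter has been initiated. Section 2.5.3 limits the primary analysis to enrolled subjects with evaluable Holter and BIOMONITOR data. Section 2.4 plans for 40% loss between consent and Holter and names both filter conditions among the reasons.

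The claim is worded as follows:

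- Summary, descriptor: "Assessment of the utility of BIOMONITOR to identify AF in ablation candidates using precise AF detection".
- Section 2, below Figure 2: the "primary analysis will focus on the utility of the BIOMONITOR for the detection of AF within patients who are being evaluated for an ablation".
- Section 2.1.1, objective: to "determine the diagnostic utility of the BIOMONITOR to detect AF within study subjects who are being evaluated for an ablation".
- Section 2.1.1, alternative hypothesis: "The Sensitivity for detecting at least one true positive AF episode per subject will be greater than 90" per cent.
- Section 2.5.1, definition: "Diagnostic sensitivity is the ability of the BIOMONITOR to correctly identify subjects who have AF as determined by the Holter monitor".

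**The concern.** Most exclusions describe the patient. These two are readings from the device being evaluated, and one of them is its own AF output. A subject whose AF the device misses throughout the observation period, and in whom nothing else counts as an AF episode, never receives a Holter and so cannot become a false negative. The quantity estimated is therefore the probability that the BIOMONITOR detects AF in the 48 hours, given AF on the Holter, at least one BIOMONITOR-recorded or transmitted AF episode beforehand, and R-wave sensing not below 0.25 mV.

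A result above 90% supports that conditional statement. Under the present wording it could be reported as sensitivity in ablation candidates generally, although up to 40 of 100 consented subjects are expected to leave before the Holter.

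**Working it through.** **1. Who can be counted.** Sections 3.1.4, 3.2, 3.2.5 and 3.3.7 remove those who fail the filter. Table 1 and 2.5.3 then confine the primary analysis to those who started the Holter. Protocol violations aside, every analysed subject has passed. Of the statements of the claim, only the phrase about study subjects in 2.1.1 can be read as carrying the condition, through Table 1.

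**2. The plan's own figures** (Section 2.4: sensitivity 97%, precision 6.35%, 95% confidence, AF prevalence on Holter 50%, later drop-out 8%).

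- AF-positive subjects: 1.96² × 0.97 × 0.03 / 0.0635² = 27.7.
- Holter subjects: 27.7 / 0.50 = 55.4, and 55.4 / 0.92 = 60.3, against the stated 60.
- Consented: 100 × (1 − 0.40) = 60.

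The sample size reproduces. The 6.35 points serve below as the yardstick for the filter's effect.

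**3. How much detectability could vary between subjects.** The only figure is in Section 1.2.1: sensitivity 95.4% ± 13.3%, first-generation device, 146 episodes in 39 subjects. The ± is not labelled. Read as a standard error over 39 subjects, it would imply an SD of 13.3 × √39 = 83%. That is impossible for a proportion with mean 0.954, whose SD cannot exceed √(0.954 × 0.046) = 20.9%. I therefore take it as a between-subject SD.

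- Largest share w of never-detected subjects for a given SD: w = r/(1 + r), with r = SD²/0.954². At SD 13.3%, r = 0.0194 and w = 1.9%.
- Some of that SD is sampling noise. The mean of 1/n is at least 39/146 = 0.267, so with no true variation noise alone gives at least 0.267 × 0.0439 = 0.0117, or 66% of the observed 0.133² = 0.0177.
- Between-subject variance is then at most (0.0177 − 0.0117)/(1 − 0.267) = 0.0081, so SD is at most 9.0% and w at most 0.9%. This assumes per-subject sensitivity is detected over true episodes.

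**4. Effect of the AF filter.** The protocol gives no AF episode rates, so these are assumed: rate L per day, gamma distributed, shape 0.3, 0.5 or 1.0, mean 0.3, 0.7 or 1.5. With per-episode detectability d, observation length T = 12 or 16 days, and a share q of otherwise failing subjects who pass through a false detection:

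- AF on Holter: 1 − exp(−2L)
- detected on Holter: 1 − exp(−2Ld)
- passes the filter: 1 − (1 − q)exp(−TLd)

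Filtered minus unfiltered sensitivity, in percentage points, by numerical integration:

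| Detectability d | q = 0 | q = 0.25 | q = 0.5 |
|---|---|---|---|
| constant 0.954 | 0.02–0.14 | 0.01–0.10 | 0.01–0.07 |
| beta, SD 13.3% | 0.15–0.63 | 0.11–0.46 | 0.07–0.30 |
| beta, SD 9.0% | 0.03–0.23 | 0.03–0.17 | 0.02–0.11 |
| 1.9% never detected, rest 97.25% | 1.90–1.96 | 1.41–1.44 | 0.92–0.95 |
| 0.9% never detected, rest 96.25% | 0.89–0.98 | 0.67–0.72 | 0.44–0.47 |

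The effect is zero if the chance of detection on the Holter does not vary between subjects. The R-wave filter is not modelled, because no figure in the protocol links R-wave amplitude to missed AF.

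The formula printed in 2.5.1 has false positives in the denominator. That is a separate matter; this working follows the verbal definition.

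**The case against.** The strongest reply is that the population is already defined. The objective speaks of study subjects, Table 1 requires that all criteria be met and the Holter started, and the filter is one of those criteria. Objectives and hypotheses normally inherit eligibility without reciting it. That stands for the objective in 2.1.1. It does not reach the descriptor or the Section 2 sentence, which speak of candidates and patients. Nor does inherited eligibility cure selection on the index test's own AF output, which bears directly on the outcome being estimated.

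Second, those who exit are not lost from view. Table 1 and 2.5.3 keep provisionally enrolled subjects in the data-of-interest population, and exit reasons are collected. This is correct, and it is why the fix is cheap.

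Third, the filter may leak more than the table allows. Section 3.1.4 accepts episodes observed or transmitted, Section 1.3.1 includes periodic and triggered strips, and Section 1.3 allows patient-triggered recordings. If AF seen on such a strip counts, a subject missed by the detector could pass and become a false negative. Section 2.4 describes the condition as absence of AF detection, so the text is not settled. Any such leakage makes the effect smaller.

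Two stronger readings are tempting. A reader might infer that the 40 planned exits conceal many missed-AF subjects and that true sensitivity is far lower. The 40 also include consent withdrawals and other reasons, and subjects without AF for 12 to 16 days would seldom be Holter-positive. A reader might also infer that sponsor-supplied reprogramming after the observation period (3.2, 3.2.6) inflates sensitivity. The protocol does not state its purpose. With an earlier predictive value of 76.3% against a sensitivity of 95.4%, the settings could equally aim at fewer false detections. Reprogramming has no established direction and forms no part of this argument.

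**Conclusion.** The point holds as a correction to the scope of the claim. The primary result is sensitivity conditional on passing a filter read from the device under test, and the protocol's statements of what will be shown do not consistently say so.

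Bias from the AF filter is probably upward and small: about 0 to 2 points, below the planned precision of 6.35. The upper end needs the extreme case in which all between-subject variation comes from never-detected subjects, none of the ± is sampling noise, and nobody passes on a false detection. The range rests on first-generation data from subjects with suspected paroxysmal or persistent AF and on assumed AF rates. It bounds the AF filter only, since the R-wave filter is unquantified.

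The documents do not show a material bias or a changed outcome of the primary test. The wording should be corrected because an over-broad conclusion would follow from the present text whatever the size of the effect.

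**What to change.** In the Summary, Section 2 (the primary-analysis sentence below Figure 2) and 2.1.1 including the hypotheses, state that the primary sensitivity result and conclusion apply to paroxysmal-AF ablation candidates with at least one BIOMONITOR-recorded or transmitted AF episode and R-wave sensing not below 0.25 mV before the Holter, and do not extend to candidates who fail either condition. The definition in 2.5.1 then follows.

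Beside the primary result, report the numbers consented, exited for no AF episode, exited for low R-wave sensing, exited for other reasons, and Holter-tested.

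The cost is a few sentences and one tabulation from exit reasons already collected under 3.2 and 3.3.7. The filter, visits and sample size do not change. The only downside is a narrower claim.
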